1.3.8.3 Resources data collected within the trial and costing methods

Costs to the National Health Service (NHS) will be estimated on the basis of the use of resources needed to implement the three proposed treatment strategies as well as those related to the subsequent use of services. Relevant costs include prescribed laxatives, consultations with GPs and nurses, and services related to the dietary and lifestyle interventions, such as the delivery of advice packages. The costs of preparing and delivering information materials and of training health care professionals in their use will also be estimated. These latter represent ‘start-up’ sunk costs, which would not be recurrent once the intervention is in place. Allowance against future savings will be made in the cost-effectiveness analysis for this initial investment.

Data on consultation rates and drugs prescribed will be collected through extraction of data from medical records of trial participants. Use of resources related to case management services and start-up costs will be gathered from the protocol, which will describe in detail how the dietary and lifestyle intervention will be delivered. Costs related to the use of medication and health services will be assigned using national published data for the United Kingdom^{24;34}.

Costs falling on the NHS will be supplemented with costs falling on patients themselves. These will be derived through telephone interviews, and will include information about the patients' purchase of over-the-counter laxatives and any other possible expenditure relating to the management of constipation (e.g. use of complementary medicine, travel costs). Where possible, participants will be asked to report costs and quantities separately.

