In both arms, this package will be delivered by practice or community nurses (according to local custom). Appointments will generally be offered at the surgery, though home visits will be an option where appropriate. In the standardised, non-personalised arm, there will be a single short (maximum of 10 minutes) appointment, with delivery of a standard pack of information and brief, general explanation of these information materials. In the personalised arm, there will be an initial long (30-45 minutes)⁵ appointment (though this may be undertaken in two shorter appointment should clinic time so dictate) and the technique of 'motivational interviewing' – 'a directive client-centred counselling style for eliciting behaviour change by helping clients to explore and resolve ambivalence'⁵ – will be employed. The personalised approach will include a patient-specific assessment of barriers to and facilitators of change and delivery of a personalised pack of information with individual targets. Patients in this arm will receive a follow-up motivational telephone call from the nurse at one week and one month after initial appointment.

A potential threat to patient recruitment and retention in this trial is patients' unwillingness to forego medication. For this reason, although diet and lifestyle will be the first-line treatment for patients allocated to those arms, the option of continuing laxative use (either prescribed or over-the-counter) will be available if required; the need for and use of such medication will be captured in patient diaries (1.3.5.1 and 1.3.5.3).

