1.3.7 Statistical analysis

Analysis will be on an intention-to-treat basis. No sub-group analyses are planned. The data will be analysed using mixed effects models, accepted practice for the analysis of data from cluster randomised trials³¹. Variation between practices and variation between patients nested within practices will be fitted as random effects. The difference between treatment strategies (i.e. the three arms of the trial will be fitted as fixed effects. Most of the outcome variables (e.g. quality of life scores, number of days with (or without) symptoms are continuous and will be analysed assuming a Normal error structure. The dependent variable in each model will be point of follow-up (three, six and twelve months outcomes for quality of life, symptoms and perceptions of bowel function; twelve months for consultation and prescription rates). For each patient, baseline data will be included as a co-variate. The mixed models will be used to generate interval estimates for the differences between alternative treatment strategies.

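### Delivery of the diet and lifestyle advice is to be costed from the protocol's description, with no per-patient count of contacts delivered, so planned-delivery costs may be set against effects of actual delivery

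*Protocol*

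**What the plan says.** Protocol section 1.3.8.3 names two sources for NHS resource use.

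- **Delivery and start-up.** "Use of resources related to case management services and start-up costs will be gathered from the protocol", a source "which will describe in detail how the dietary and lifestyle intervention will be delivered".
- **Consultations and drugs.** "Data on consultation rates and drugs prescribed will be collected through extraction of data from medical records of trial participants". Section 1.3.5.3.5 sets this abstraction at the twelve months after recruitment, for all participants.

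The same section lists as relevant costs "consultations with GPs and nurses, and services related to the dietary and lifestyle interventions, such as the delivery of advice packages". It gives no rule for keeping the two kinds of nurse contact apart.

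Section 1.3.3.1 describes planned delivery by practice or community nurses. Standardised advice is one appointment of at most 10 minutes. Personalised advice is an appointment of 30-45 minutes, "though this may be undertaken in two shorter appointment should clinic time so dictate", plus telephone calls at one week and one month whose length is not given. In both arms "home visits will be an option where appropriate". Section 1.3.5.4 places the first appointment at W1 and the calls at W2 and W5.

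For effects, section 1.3.7 states: "Analysis will be on an intention-to-treat basis".

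**The concern.** Intention-to-treat effects reflect the intervention as patients received it, including missed calls, split visits and home visits. A cost taken from the description of delivery reflects the intervention as planned. A cost-effectiveness ratio should have both on the same footing.

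The second objective (section 1.2.1) asks for the cost-effectiveness of standardised against personalised advice. Nurse contact time is a main planned difference in resource use between those arms. Section 1.3.8.4 adds that, if no strategy is shown to be superior on utilities or discomfort-free days, the cheaper strategy will be recommended. Cost alone would then carry the recommendation.

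A second, smaller issue is that the advice visit is a nurse contact inside the record-abstraction window, so it could enter the NHS cost once from each source.

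**Working it through.** The protocol states no cost figure, so there is none to reproduce. The check has three parts.

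**1. Is delivered contact captured anywhere for costing?**

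- The W3-4 fidelity questionnaire (sections 1.3.5.3.4 and 1.3.5.4) goes to a small sample and monitors the content of the advice.
- The telephone interviews at W13 and W26 collect patients' own costs and their personal success in managing constipation.
- The record abstraction (section 1.3.5.3.5) collects consultation rates and laxative prescriptions. It may pick up the first visit, but it names no field for reinforcement calls, split appointments or place of visit.

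None gives a per-patient count of calls, split visits or home visits.

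**2. How far could planned and delivered nurse time differ?**

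Inputs from section 1.3.3.1: personalised visit L = 30 or 45 minutes; two calls; standardised visit 10 minutes (the stated maximum). Assumed, because the protocol gives no figures: call length c = 5 or 10 minutes; share of visits that occur, v, equal in both arms; share of calls that occur, k.

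Planned increment = L + 2c − 10. Delivered increment = vL + 2kc − 10v.

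| L, c (min) | Planned | Delivered, v = 1, k = 0.6 | Overstated by | Delivered, v = 0.8, k = 0.6 | Overstated by |
|---|---|---|---|---|---|
| 30, 5 | 30+10−10 = 30 | 30+6−10 = 26 | 15% | 24+6−8 = 22 | 36% |
| 45, 10 | 45+20−10 = 55 | 45+12−10 = 47 | 17% | 36+12−8 = 40 | 38% |
| 30, 10 | 30+20−10 = 40 | 30+12−10 = 32 | 25% | 24+12−8 = 28 | 43% |
| 45, 5 | 45+10−10 = 45 | 45+6−10 = 41 | 10% | 36+6−8 = 34 | 32% |

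The first two rows pair the short visit with short calls and the long visit with long calls, giving 15-17% and 36-38%. The other pairings widen these to 10-25% and 32-43%.

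Other assumed rates move the result further. With all visits, 75% of calls, L = 45 and c = 5, the ratio is 45/(45+7.5−10) = 45/42.5, or 6% over. With 80% of visits, 50% of calls, L = 30 and c = 15, it is 50/(24+15−8) = 50/31, or 61% over.

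The sign is not fixed. In the first two rows with all visits made, the shortfall is 30−26 = 4 and 55−47 = 8 minutes per patient. If home visits, split appointments or overruns add more than that on average to the personalised arm, over and above what they add to the standardised arm, planned costing is too low.

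**3. Could the first visit be counted twice?**

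The visit is at W1, and the abstraction covers twelve months from recruitment. If a recorded visit were costed at its full length on top of the planned figure, the increment would rise by (L − 10)/(L + 2c − 10). For c = 5 or 10 this runs from 20/40 = 50% to 35/45 = 78%. If recorded visits were instead costed at one flat rate per consultation, a single extra visit would add the same amount to both advice arms and cancel between them. It would still inflate both against the laxative arm, whose W1 visit comes only from records.

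**The case against.** The strongest reply is that section 1.3.8.3 also takes consultations from medical records. It can be read as counting attended visits from records and using the protocol only for content and unit times, which is close to the fix proposed here. The term for the services to be costed from the protocol is undefined, and the protocol referred to could be a more detailed operational document. Patients who withdraw at the first appointment have their data destroyed (sections 1.3.5.3.1 and 1.3.5.4), so some non-attendance leaves the data set. Section 1.3.8.2 promises disaggregated resources and costs, and section 1.3.8.5 promises sensitivity analysis on key inputs. How to separate intervention visits from ordinary ones could be left to an analysis plan, which is not at hand.

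Much of this stands. A reader might infer that every advice-arm patient will be charged the full set of contacts whether or not they took place, or that visits will be counted twice. The text supports neither: first visits may be captured as attended, and double counting happens only if practices record the visit as a consultation and the two sources are added without reconciliation, which an analyst would probably notice.

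What does not answer the point is the rest of delivery. Whichever document is meant, it describes how delivery will be done. Calls, split visits and home visits have no per-patient source. This is a choice of what to collect, so a later analysis plan could not recover it, and the sensitivity analysis would have no observed delivery data to use.

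**Conclusion.** The point holds in conditional form. If delivery is costed from the description of planned contacts, costs and effects rest on different delivery, and the personalised-minus-standardised cost increment is misstated. The percentages above illustrate the possible size and do not estimate it: call length, visit attendance and call completion are all assumed, and they concern nurse minutes only. The lower illustration fits better to the extent that non-attenders withdraw and leave the data; the higher one needs non-attenders who remain in the analysis.

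Two stronger conclusions are not supported. The documents do not show that costs would be overstated, because home visits and extra time work the other way. Nor do they show that the ranking of the two advice arms would change: in every row of the table personalised advice still takes at least 22 minutes more nurse time. At stake is the size of the increment and, through it, the cost-effectiveness ratio, together with the comparison of each advice arm with laxatives. The primary outcome analysis is unaffected. This is a cheap improvement to a stated objective.

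**What to change.** In section 1.3.5.3.5, add fields to the record abstraction for intervention contacts: number of advice appointments, surgery or home, and whether the W2 and W5 calls were made. In section 1.3.8.3:

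- cost the contacts delivered to each participant in the main analysis, using protocol durations only as unit times, with 30 and 45 minutes as bounds for the personalised visit;
- flag these contacts so that they are not also costed as ordinary nurse consultations;
- keep full planned delivery as a sensitivity analysis;
- leave start-up and training costs based on the protocol.

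The cost is a few extra fields in an abstraction that research nurses will already carry out for every participant. The drawback is that some calls may not be recorded, so delivered contact could be undercounted; the full-delivery sensitivity analysis bounds that. No clinical procedure changes.

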1.3.8.4 Synthesis of costs and outcomes

If there is not statistically and clinically significant evidence that one treatment strategy is superior to another in terms of health utilities or DFDs, a cost-minimisation framework will be used and the adoption of the less expensive strategies will be recommended. Similarly, recommendations for adoption will be made if one strategy appears to be more effective and less costly than its comparator(s). If one strategy appears to be more effective but more expensive than its comparator(s), estimates of incremental cost-effectiveness ratios will be generated and compared. A judgement will be required in a policy-making context to establish whether the additional benefits warrant the additional costs. In any case, results will be presented taking into account the issues of the generalisability of the results to other local settings.

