1.3.5 Assessment of outcomes

1.3.5.1 Outcome measures

The primary outcome, and the criterion upon which the sample size calculations have been based, is patient-reported condition-specific quality of life at three months post recruitment (1.3.5.2). Our preferred measure of quality of life is the constipation-specific PAC-SYM / PAC-QOL²⁵, which has been demonstrated to have good validity and reliability. However, this measure is not utility-based. For the purposes of the economic evaluation (1.3.8), a measure of the utility placed by patients on

their health state will be required. The condition-specific measure of quality of life will therefore be supplemented by the generic, utility-based EQ-5D^{26;27}.

Secondary outcomes will include: bowel movement frequency; the presence/absence of the other Rome criteria for constipation; patients' own perceptions of whether or not they are constipated; patient satisfaction with bowel function; adverse effects of treatment; relapse / re-consultation rates; fluid and fibre intake (Table 1).

In addition, the cost implications of the condition and its treatment (e.g. GP consultations, purchase of prescribed and over-the-counter medication) will be assessed, as part of the economic evaluation (Table 2; section 1.3.8).

Table 1 Outcome measures

Primary outcome	Measurement method	When	Where
Health-related quality of life	Postal questionnaire	At three months post recruitment	Participant's home
Secondary outcomes	Measurement method	When	Where
Health-related quality of life	Postal questionnaire	At six and twelve months post recruitment	Participant's home
Number of bowel movements per week	Self-completed structured diary + Postal questionnaire	Daily for 6 months At 12 months	Participant's home
Other Rome criteria: straining at defecation, stool consistency, perceived incomplete evacuation	Self-completed structured diary + Postal questionnaire	Daily for 6 months & for 1 week at 12 months At 12 months	Participant's home
Subjective perception of whether constipated; satisfaction with bowel function	Telephone interview + Postal questionnaire	At 3 months At 6 months & 12 months	Participant's home
Adverse events: abdominal pain, nausea, bloating, flatulence, diarrhoea	Self-completed structured diary + Postal questionnaire	Daily for 6 months & for 1 week at 12 months At 12 months	Participant's home

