It is important to note that the LIFELAX trial is not a comparison of an intervention with placebo or with normal practice. Instead, there are three active treatment groups. It is not unreasonable to assume that we might observe at least a small change over time in symptom-related and quality of life outcomes in all of these treatment groups. What we are primarily interested in is whether one intervention offers a relative advantage over the others. For example, if the changes over time for the laxative and standardised diet and lifestyle interventions were 'small' by the established criteria set out above, but a 'moderate' improvement was observed in the individualised diet and lifestyle arms, we might reasonably conclude that this intervention offered a relative advantage.

For an effect size of 0.3, 90% power, a significance level of 5%, an intra-class correlation of 0.04, and the ability to recruit and retain 25 patients per practice, we therefore need a total of 57 practices (19 per arm).

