1.3.8.2 Measure of benefits used and type of study

Considering all the measures of effectiveness estimated within the clinical trial, a cost-consequence analysis³³ will be outlined alongside the cost-effectiveness analysis. In the cost-consequence analysis, clinical and QoL profile scores, resources used for the implementation of the intervention strategies and related costs will be presented in a disaggregated way. For each arm of the trial, the breakdown of costs and outcomes will be listed in a tabular format; no summary measures will be presented. This type of evaluation and presentation provides readers with a more transparent interpretation of the results and allows them to make a more selective application of the findings to specific decision-making contexts.

Although quality of life is an important indicator of benefit in the treatment of constipation, and is the primary outcome measure in this study, none of the currently available condition-specific measures yield a unique QoL score. A comparison/synthesis of costs and outcomes based on each of the separate QoL dimensions in our chosen profile measures would be methodologically invalid. For this reason, a utility-based, index measure – the EQ-5D^{26;27} – will also be used, to facilitate calculation of Quality Adjusted Life Years (QALYs). We are, however, aware of the concerns about the use of QALYs in devising resource allocation strategies between different age cohorts. Therefore, we aim to develop or apply already existing ‘corrective’ measures to the results we will obtain, so that our findings will not have unfavourable implications for the funding of health technologies for older people.

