Furthermore, we anticipate that the EQ-5D may not be sensitive enough to detect differences in the population being studied. Therefore, alongside this utility-based measure, we will calculate discomfort-free days (DFDs) as a new measure of outcome. This measure will include the impact on patients’ wellbeing of unwanted symptoms due to both constipation and treatment side-effects. It will be a crude but meaningful measure of the patients’ perceived effectiveness of treatment. DFDs will be derived through the self-completed structured diaries, in which patients will be asked to report the overall impact of both the symptoms of constipation and side-effects of the laxatives on their wellbeing. Severity of impact will be graded in levels, and the number of days spent in each level of discomfort will be calculated. This information will be used to assess correlation with DFDs responses. We believe that the comparison of DFDs with EQ-5D utilities will represent a useful addition to the body of knowledge on the assessment of cost-effectiveness in trials where the main impact is expected to be on palliation of symptoms and improvement of the quality of life, rather than on extension of life.

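### The economic decision rule in 1.3.8.4 treats failure to show superiority in utilities or discomfort-free days as equal effect, and then recommends the less expensive strategies

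*Protocol*

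**What the plan says.** Protocol section 1.3.8.4 sets out how costs and outcomes lead to a recommendation. The condition is: "If there is not statistically and clinically significant evidence that one treatment strategy is superior to another in terms of health utilities or DFDs". The consequence is: "a cost-minimisation framework will be used and the adoption of the less expensive strategies will be recommended". The section gives no equivalence or non-inferiority margin for either measure and attaches no condition to the interval around the effect.

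Section 1.3.8.2 describes the two measures that drive the rule. On utilities: "we anticipate that the EQ-5D may not be sensitive enough to detect differences in the population being studied". DFDs are introduced as a new measure, with this comment: "It will be a crude but meaningful measure of the patients’ perceived effectiveness of treatment".

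The trial was sized on something else. Section 1.3.5.1 states: "The primary outcome, and the criterion upon which the sample size calculations have been based, is patient-reported condition-specific quality of life". Section 1.3.6.3 gives the inputs as "For an effect size of 0.3, 90% power, a significance level of 5%, an intra-class correlation of 0.04". With 25 patients kept in each practice, it arrives at 57 practices, 19 per arm.

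**The concern.** Cost-minimisation is sound only when effects are known to be near enough equal. Here it is entered because superiority was not shown, which also happens when the data are too imprecise to tell. Requiring both statistical and clinical significance does not help: failing either one triggers the rule, so a clinically relevant but imprecise difference is handled as no difference.

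The rule is also lopsided. When one strategy appears more effective and dearer, 1.3.8.4 leaves the trade-off to policy judgement. When the evidence on effect is weakest, it recommends adoption outright.

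Comparative cost-effectiveness is the commissioned question (1.1) and part of both objectives (1.2.1). Section 1.2 expects personalised interventions to be typically more resource-intensive, so an inconclusive result would tend to count against that arm. What is at stake is an adoption recommendation that rests on lack of precision.

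**Working it through.** The fault is one of logic and does not depend on numbers. The arithmetic below only shows how much room the planned trial leaves for it.

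**1. The plan's own figure.** Inputs from 1.3.6.3: 0.3 SD, 90% power, 5% significance (two-sided assumed, as the side is not stated), ICC 0.04, 25 patients per practice.

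- Patients per arm without clustering: 2 × (1.960 + 1.282)² / 0.3² ≈ 234.
- Design effect: 1 + (25 − 1) × 0.04 = 1.96.
- 234 × 1.96 = 458.6; 458.6 / 25 = 18.35, rounded up to 19 per arm, or 57 practices.

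The stated 57 is reproduced.

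**2. Precision of one pairwise comparison at that size.** The protocol gives no SD, ICC or target difference for EQ-5D or DFDs. I assume they share the primary outcome's ICC and retention, and work in SD units. The ICC range is 0.04 (used in the calculation) to 0.05 (called typical in the same section). Patients per arm: 19 × 25 = 475.

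- SE = √(2 × design effect / 475).
- ICC 0.04: √(2 × 1.96 / 475) = 0.091 SD; 95% half-width 1.96 × SE = 0.178 SD.
- ICC 0.05, design effect 2.20: √(2 × 2.20 / 475) = 0.096 SD; half-width 0.189 SD.

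A just non-significant estimate lies about one half-width from zero, so its interval reaches about 2 × 0.178 = 0.36 SD or 2 × 0.189 = 0.38 SD. Both exceed the trial's 0.3 SD target.

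**3. Chance of a non-significant result, one comparison, one measure.** This is 1 − Φ(d/SE − 1.96), less a negligible opposite tail.

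| True difference | ICC 0.04 | ICC 0.05 |
|---|---|---|
| 0.20 SD | 0.405 | 0.453 |
| 0.25 SD | 0.214 | 0.262 |
| 0.30 SD | 0.090 | 0.124 |

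Section 1.3.6.3 calls effects below 0.2 negligible and 0.2 up to 0.5 small. It states this for change over time, so applying it to a difference between arms is a further assumption.

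**4. The word joining the two measures.** It is unclear whether the rule needs failure on utilities and on DFDs, or on either. If both must fail and the true difference is 0.2 SD on each, the chance runs from 0.405² = 0.16 or 0.453² = 0.21 (independent measures) up to 0.405 or 0.453 (perfectly correlated). If failure on either is enough, it is at least the single-measure figure. The added clinical-significance condition can only raise these chances; it is not modelled because no threshold is given.

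**5. Could a null result establish equality?** With a true difference of zero and two one-sided tests at 2.5% each, power is 2Φ(margin/SE − 1.96) − 1. For an assumed 0.2 SD margin this is 0.19 (ICC 0.04) or 0.09 (ICC 0.05). For an assumed 0.3 SD margin it is 0.82 or 0.75.

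**The case against.** The best defence is that the estimates do not disappear. Section 1.3.7 promises interval estimates for differences between strategies. Section 1.3.8.2 promises a cost-consequence table for every arm, and 1.3.8.5 a sensitivity analysis covering uncertainty in assumptions, methods and data. A reader might infer from 1.3.8.4 that the estimated effect is thrown away whenever p exceeds 0.05; these sections show that it is not. They do not change the recommendation, though. The intervals are not tied to the economic rule, and the one specific provision in 1.3.8.5 for non-significant differences concerns resource use, not effects.

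Second, the size should not be overdrawn. At 0.3 SD the trial would miss significance only 9 to 12% of the time under the same assumptions. Differences below 0.2 SD are ones that the protocol itself calls negligible, and if both measures must fail the rule fires less often. All of this stands, and it limits the size of the problem without removing it.

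Third, two further charges are tempting and not supported. Section 1.3.8.2 plans corrective measures for QALYs "so that our findings will not have unfavourable implications for the funding of health technologies for older people", which might be read as adjusting results towards a preferred answer. The stated worry is fairness between age cohorts. All three arms enrol people aged 50 or over, and nothing indicates that one arm would gain. No significance test is involved, so it is not the same fault. A reader might also argue that laxative use allowed in the advice arms dilutes the contrast and makes the rule fire more readily. In a pragmatic, intention-to-treat trial that use is part of the strategies being compared, so a smaller difference is their effect and not a distortion of it.

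**Conclusion.** The concern holds, limited to the decision rule in 1.3.8.4. Absence of demonstrated superiority leads directly to a recommendation on cost, with no margin and no interval condition. The measures that trigger it are ones whose sensitivity or maturity the protocol questions, and for which no sample size was calculated. This is a rule that the protocol itself fixes, not a detail left to an analysis plan.

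The illustrative size is a 40 to 45% chance of non-significance at a true 0.2 SD for one pairwise comparison on one measure, 9 to 12% at 0.3 SD, and a just non-significant result compatible with about 0.36 to 0.38 SD. These figures assume a two-sided 5% test, 19 × 25 patients per arm, and the primary outcome's ICC and retention for EQ-5D or DFDs. They fall if both measures must fail. The primary clinical analysis, the sample size and the data collection are not affected.

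**What to change.** In 1.3.8.4, remove non-significance as the trigger for cost-minimisation. In all cases estimate incremental cost and incremental effect jointly, allowing for clustering by practice, and report the uncertainty whatever the p-values, for example as incremental net benefit with intervals or as acceptability curves for the three strategies.

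If cost-minimisation is kept, allow it only when the interval for the effect lies within an equivalence margin set before outcome data are seen, and say whether this must hold for utilities, for DFDs or for both. At the planned size that condition would rarely be met with a margin as tight as 0.2 SD (power 9 to 19% at a true difference of zero), so the joint analysis should be the main route.

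The cost is a rewording of one section and modest extra analysis, with no new data. The downside is a recommendation that may be less clear-cut.

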1.3.6.3 Sample size

Participating practices will be randomised to one of three arms. In calculating sample size for cluster randomised trials³¹, it is necessary to take into account within-cluster variance, measured

by an intra-class correlation (ICC). Our experience in previous studies suggests that intra-class correlations of 0.05 for quality of life outcome are typical.

Preliminary analysis of data from the average-sized practices of one of the applicants suggests that there will be approximately 40 patients in such a practice meeting eligibility criteria (1.3.4). We recognise that patients in practices allocated to the diet and lifestyle arms of the trial may be reluctant to undertake a change to their diet or lifestyle and may therefore withhold consent to participate. It is in anticipation of this risk that we have made the assumption that only 30 out of 40 patients identified will agree to participate and that only 25 will provide follow up data for 12 months.

Our primary outcome is a continuous variable – score on a quality of life (QoL) scale. In the absence of detailed data on the distribution of QoL scores in our population, we can nonetheless specify the effect size that we wish to detect. We arbitrarily set this at 0.3 standard deviations on the condition-specific quality of life scale. Within the literature on quality of life assessment, there is a growing consensus³² that an effect size (i.e. change over time divided by standard deviation at baseline) of less than 0.2 represents a negligible change, an effect size of 0.2 up to 0.5 represents a 'small' effect, an effect size of 0.5 up to 0.8 represents a 'moderate' change and an effect size of in excess of 0.8 represents a 'large' change. These criterion values, which have been shown to be stable across a range of settings, have been established by reference to what clinicians and patients consider to be an 'important' difference – the emphasis is therefore on clinical rather than statistical significance. Our proposed effect size of 0.3 therefore represents the difference between the threshold values for 'small', 'moderate' and 'large' changes (0.5 – 0.2; 0.8 – 0.5).

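### The rule for recommending the cheaper strategy never checks the primary outcome, so the trial could report a primary benefit and still recommend the cheaper arm

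*Protocol*

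**What the plan says.** Section 1.3.8.4 turns results into recommendations. Its first condition reads "If there is not statistically and clinically significant evidence that one treatment strategy is superior to another", and it continues "in terms of health utilities or DFDs, a cost-minimisation framework will be used and the adoption of the less expensive strategies will be recommended". Later sentences of that section cover a strategy that is more effective and cheaper (recommend it) and one that is more effective but dearer (estimate incremental cost-effectiveness ratios and leave the judgement to policy-makers).

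The primary outcome is defined in 1.3.5.1: "The primary outcome, and the criterion upon which the sample size calculations have been based, is patient-reported condition-specific quality of life at three months" after recruitment. It is the only outcome with a power calculation (1.3.6.3).

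Section 1.3.8.2 explains the choice of economic outcomes. The condition-specific instruments give a profile and not one score, so combining costs with each dimension is held to be invalid, and EQ-5D is added to allow QALYs. The section then says "we anticipate that the EQ-5D may not be sensitive enough to detect differences in the population being studied", and for that reason adds DFDs from the patient diary, described as crude but meaningful. The condition-specific scores appear in a disaggregated cost-consequence table that carries no decision rule.

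**The concern.** Cost-minimisation assumes that the strategies are equally effective. Section 1.3.8.4 makes that assumption from EQ-5D and DFDs alone. Nothing in the protocol stops the cheaper arm being recommended when the primary outcome differs between arms. The sensitivity analysis in 1.3.8.5 mentions non-significant differences in resource use but not the primary outcome.

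The protocol's own example shows how this could happen. Section 1.3.6.3 says that a moderate improvement in the personalised arm, against small changes in the other two, would reasonably be read as a relative advantage. Section 1.2 says personalised interventions typically use more resources. If EQ-5D and DFDs are both non-significant in that scenario, 1.3.8.4 points to a cheaper arm. The trial would then give two opposed answers to the commissioned question, and the recommendation would rest on outcomes for which no power is stated.

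**Working it through.** **Reproducing the stated size.** Inputs from 1.3.6.3: "For an effect size of 0.3, 90% power, a significance level of 5%, an intra-class correlation of 0.04" and 25 patients retained per practice.
- Patients per arm without clustering: 2 × (1.96 + 1.2816)² / 0.3² = 233.5, rounded up to 234.
- Design effect: 1 + (25 − 1) × 0.04 = 1.96.
- Practices per arm: 234 × 1.96 / 25 = 18.35, rounded up to 19, so 57 in total. This matches the protocol, taking the 5% as two-sided.

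**Precision at that size.**
- Patients per arm: 19 × 25 = 475. Effective number: 475 / 1.96 = 242.3.
- SE of a pairwise difference: √(2 / 242.3) = 0.0908 SD.
- Power, from Φ(d/SE − 1.96) plus a negligible opposite tail: 91% at 0.30 SD, 60% at 0.20 SD, 38% at 0.15 SD, 20% at 0.10 SD.

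**How often the rule and the primary result could part.** The protocol gives no effect size, SD or important difference for EQ-5D or DFDs, so the following are assumptions:
- a true primary benefit of 0.30 SD;
- ICC 0.04 for all three outcomes;
- correlations of 0.3, 0.5 and 0.7 between the test statistics;
- the rule is triggered when neither economic outcome is significant.

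The test statistics were simulated as trivariate normal with means d/0.0908 and unit variances (500,000 or more draws per setting). The last column is the probability that the primary is significant and both economic outcomes are not.

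| EQ-5D effect | DFD effect | Probability |
|---|---|---|
| 0.30 SD | 0.30 SD | 1–2% |
| 0.15 SD | 0.30 SD | 5–6% |
| 0.15 SD | 0.25 SD | 13–14% |
| 0.20 SD | 0.20 SD | 17–21% |
| 0.15 SD | 0.15 SD | 37–41% |
| 0.10 SD | 0.10 SD | 60–63% |

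Two things push these figures in opposite directions. They give the chance that the results disagree; a contradictory recommendation also needs the better arm to be the dearer one. They also ignore the added requirement of clinical significance, which has no stated threshold for either economic outcome and makes the rule easier to trigger.

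**The case against.** The exclusion is reasoned, not an oversight. Section 1.3.8.2 says why the condition-specific measure is kept out of the cost synthesis. That stands as a reason not to form a cost-effectiveness ratio on it. It does not extend to the assumption of equal effectiveness, which needs only a comparison between arms, and 1.3.6.3 itself treats the primary outcome as a continuous score on a scale.

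DFDs were added to guard against an insensitive EQ-5D. They come from a diary kept daily for six months and cover both constipation symptoms and side-effects. Nothing in the protocol suggests that they respond as weakly as a generic utility index. This objection stands, and it limits the size of the problem: if DFDs respond as strongly as the primary outcome, disagreement is rare.

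The primary result is not hidden. It is analysed with interval estimates (1.3.7) and set beside costs in the cost-consequence table, so decision-makers would see a clash. That also stands, but the table has no rule attached and 1.3.8.4 does.

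A reader might also infer that naming utilities or DFDs leaves open which one decides. The ordinary meaning is that no strategy is superior on either, so the trigger is clear when only one of them is significant.

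**Conclusion.** The point holds: a rule stated in the protocol can recommend the cheaper arm against a significant result on the outcome the trial is sized for, and nothing in the text prevents it. It requires the arm that is better on the primary outcome to be dearer.

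A reader might infer that such a contradiction is likely, for instance from the 37–41% figure. The documents do not support that. The figure needs DFDs to be attenuated as much as EQ-5D, and the protocol anticipates poor sensitivity only for EQ-5D. The defensible range runs from 1–2% to about 60% according to assumed effects, and the protocol gives nothing with which to narrow it. The fault is therefore a gap in the rule with a possible but unquantified consequence. It should be fixed because the fix is cheap.

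**What to change.** Add to 1.3.8.4 that, for any pair of arms, no strategy is recommended on cost alone when the three-month primary contrast, on the pre-specified primary score or scores, shows a significant difference in favour of the dearer strategy. In that case, report incremental costs beside the primary result in the cost-consequence table, give the incremental cost per QALY and per DFD with their uncertainty, and leave the judgement to policy-makers, as the section already does for dearer, more effective strategies.

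Requiring the primary interval to lie within 0.3 SD is a tempting alternative but a poor one. Section 1.3.6.3 set 0.3 arbitrarily, as an effect to detect and not as an equivalence margin, and 1.3.8.2 says there is no single score to apply it to. It could also let through the very case at issue. If baseline explained 36% of the variance (an assumption), the SE would be 0.0908 × √0.64 = 0.0727 SD. Estimates from 1.96 × 0.0727 = 0.142 up to 0.3 − 0.142 = 0.158 SD would then be significant and still pass.

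The cost is a change of wording, with no new data. The downside is fewer clear-cut cost-minimisation recommendations.
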